## 1.5 Study Rationale

Laparoscopic, minimally invasive surgery has become standard treatment for several benign and malignant diseases including endometrial or colorectal cancer because of reduced bleeding, less complication rates, shorter hospital stays and lower costs while achieving same oncological safety. After publication of the LACC study, multiple gynecologic oncologists abandoned LRH from their clinical routine. Others criticize study methodology and surgical techniques which were not standardized and suggest strategies to improve outcomes after LRH. Important results of recently published retrospective national and international studies by Köhler, Chiva and Kong et al. demonstrated that the outcomes of laparoscopic surgery were comparable to open surgery when no uterine manipulator, vaginal colpotomy and vaginal cuff closure were performed. Although patient and tumor characteristics are not completely comparable between those different studies, these results raise the strong hypothesis that outcomes of laparoscopic radical hysterectomy depend on surgical technique and the possibility of tumor cell spread into the intraperitoneal cavity. The updated German S3 guideline emphasizes these very good oncological results of preventive operative measures which underline the hypothesis of necessary surgical tumor hygiene and recommend the validation by randomized studies. Therefore, only a well-designed, well-powered and stringently conducted study with expert

centers can finally answer the question whether LRH is an oncological equivalent and less invasive alternative to ARH in early stage cervical cancer.

The idea of minimal invasive surgery is that patients gain significant profit from decreased morbidity, less pain, shorter hospital stays and faster recovery. Therefore, potential adjuvant therapies like radiation or chemotherapy can be administered directly after the primary treatment due to decreased risks for perioperative complications such as wound healing disorders. Furthermore, the reduced lower socioeconomic burden of laparoscopy is linked to indirect costs with earlier return to work and increased work productivity. The main aim of the G-LACC trial is to prove that laparoscopic hysterectomy is non-inferior to abdominal hysterectomy with regard to safety and disease-free survival. Thus, the G-LACC trial will have significant clinical impact on the future surgical approach for early cervical cancer.

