### Complications and treatment-associated morbidity

Intra- and post-operative treatment-related complications are recorded. In addition, other serious adverse events (SAEs) are captured at each visit starting with surgery (section 6).

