#### 5.3.7 Record post-operative complications

Please record post-operative complication and state if any of the following adverse events occurred: abdominal pain, constipation, fatigue, paresthesia, peripheral sensory neuropathy, urinary incontinence, urinary retention, dyspareunia, pelvic pain, lymphedema, hot flashes.

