#### 5.3.15 Safety assessments (intra-/post-operative complications, SAEs)

Treatment related intra-operative complications will be recorded on the day of surgery (visit 3) according to the definition of Rosenthal (see Appendix 12.1).

Treatment related post-operative complications will be recorded starting directly after surgery up to one year thereafter with a first assessment 30 days post-surgery (visits 4 to 6).

Furthermore, other particularly not treatment related serious adverse events (SAEs) will be captured from the day of surgery until one year post surgery (visits 3 to 6). For a detailed definition of SAEs and the recording procedure see sections 6.1 and 6.2. Note that the reporting of all serious adverse events is mandatory for the investigator within 24 hours after awareness (see section 6.2).

SAEs have to be reported in the eCRF. Serious adverse events will be reported anually to the Ethics Committee according to the Declaration of Helsinki.

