#### 6 ADVERSE EVENTS

#### 6.1 Definition of Serious Adverse Events

Serious Adverse Event Definition

A Serious Adverse Event (SAE) is defined as any undesirable medical occurrence according to the FDA definition:

- Results in death
- Is life threatening

Report if you suspect that the death was an outcome of the adverse event and include the date. Report if suspected that the patient was at substantial risk of dying at the time of the adverse event.

• Requires hospitalization (initial or prolonged)

Report if admission to the hospital or prolongation of hospitalization was a result of the adverse event. Emergency room visits that do not result in admission to the hospital should evaluated for one of the other serious outcomes (e.g., life-threatening; required intervention to prevent permanent impairment or damage; other serious medically important event).

• Results in disability or permanent damage

Report if the adverse event resulted in a substantial disruption of a person's ability to conduct normal life functions, i.e., the adverse event resulted in a significant, persistent or permanent change, impairment, damage or disruption in the patient's body function/structure, physical activities and/or quality of life.)

• Other serious (important medical events)

Report when the event does not fit the other outcomes, but the event may jeopardize the patient and may require medical or surgical intervention (treatment) to prevent one of the other outcomes. Examples include for instance the development of drug dependence or drug abuse as a result of the study treatment.

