#### Assessment of Intensity and Causality

The investigator will assess the intensity for each SAE reported from day of surgery until the follow up visit 6. An event is defined as 'serious' when it meets at least one of the predefined outcomes as described in the definition of an SAE, NOT when it is rated as severe.

Furthermore, the investigator is obligated to assess the relationship between trial treatment and each occurrence of SAE. The investigator will use clinical judgment to determine the relationship. Alternative causes, such as underlying disease(s), concomitant therapy, and other risk factors, as well as the temporal relationship of the event to trial treatment will be considered and investigated. For each SAE, the investigator must document in the medical notes that he/she has reviewed the SAE and has provided an assessment of causality. The investigator may change his/her opinion of causality in light of follow-up information and send a SAE follow-up report with the updated causality assessment to the responsible investigator.

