## 9.5 Selection of participating trial sites and surgeons

In order to guarantee optimal, representative and reliable study results this trial will be conducted in compliance with strict quality criteria. Therefore, all trial sites and surgeons outside the primary investigating center must be approved by the Trial Steering Committee ensuring adherence to protocol.

Prior to participation each interested trial site has to submit a quality assessment form (see Appendix 12.3) to the TSC indicating the site's annual volume of surgical gynecologic oncology cases and surgical cervical cancer cases as well as information regarding the general infrastructure of the center (e.g. ability to perform ultrastaging). Furthermore, each surgeon must submit 10 anonymized surgery reports accompanied by their histopathology reports (if present) from both abdominal and laparoscopic surgeries including pelvic lymphadenectomies of malignancies of the uterus.

It is at the discretion of the TSC to select or deselect individual surgeons from participating in the trial. Only surgeons stated in the quality assessment form are allowed being lead surgeons, amendments during the trial can be made.

During the study, it is at the discretion of the TSC to request on-site audits (For-Cause-Audits) or videos of procedures, to close centers with a higher than average rate of postoperative major complications or poor quality of surgery, from further accrual, temporarily of irrevocably after consultation with the DMC.

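### SAE capture is described both as events other than treatment-related ones and as all SAEs, and post-operative complications carry no named severity grade from which the undefined term major could be derived

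*Protocol*

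**What the plan says.** **SAE capture.** Section 2.3.2 (complications and treatment-associated morbidity) first has treatment-related intra- and post-operative complications recorded, then adds: "In addition, other serious adverse events (SAEs) are captured at each visit starting with surgery". Section 5.3.15 follows the same order. Treatment-related intra-operative complications are recorded at visit 3 and treatment-related post-operative complications at visits 4 to 6. After that, "other particularly not treatment related serious adverse events (SAEs) will be captured from the day of surgery until one year post surgery".

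The same section continues: "Note that the reporting of all serious adverse events is mandatory for the investigator within 24 hours after awareness". Section 6.1 sets no condition on relatedness: "A Serious Adverse Event (SAE) is defined as any undesirable medical occurrence according to the FDA definition". Under Assessment of Intensity and Causality in 6.2, "the investigator is obligated to assess the relationship between trial treatment and each occurrence of SAE".

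**Complication severity.** Section 5.3.7 has an open instruction to record the post-operative complication, followed by a checklist: "abdominal pain, constipation, fatigue, paresthesia, peripheral sensory neuropathy, urinary incontinence, urinary retention, dyspareunia, pelvic pain, lymphedema, hot flashes". It names no grade. Intra-operative complications are graded 0 to IV (5.3.5, Appendix 12.1), and lymphatic effects are graded by CTCAE 3.0 (5.3.13, Appendix 12.2).

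**Use of the data.** Section 7.1.3 compares SAE frequencies between arms by chi-squared tests, assessed descriptively. Section 9.2 gives SAE incidence rates as an example of what may prompt an extra DMC review. Section 9.5 gives the steering committee discretion "to close centers with a higher than average rate of postoperative major complications" or poor surgical quality. Section 9.3.3 allows recruitment at a centre to be stopped on similar grounds, but its threshold is an elevated occurrence.

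**The concern.** Complications and treatment-associated morbidity are a secondary objective (2.2). They are also the benefit that section 1.6 sets against the oncologic risk of minimally invasive surgery, and section 1.5 expects "decreased risks for perioperative complications such as wound healing disorders". Section 1.4 reports that the earlier randomized trial found no reduction in complications with laparoscopy, so this trial has to measure that benefit rather than assume it.

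Two things stand in the way. First, sites are given two descriptions of what belongs in the SAE record. If they resolve the conflict differently, SAE counts differ between sites for reasons unrelated to surgery. Second, the post-operative complication record carries no severity, so a trivial and a serious complication look alike in it. Neither can be repaired in a later analysis plan: an event not reported as an SAE, or a grade never collected, cannot be recovered at analysis.

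**Working it through.** The protocol states no rate for SAEs or complications, so there is no figure of its own to reproduce on this point. The check is mainly a comparison of sections.

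**Step 1: which serious events belong in the SAE record?**

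| Section | Rule | Treatment-related serious event included? |
|---|---|---|
| 2.3.2 | SAEs are those other than treatment-related complications | Reads as no |
| 5.3.15, capture sentence | The same, with emphasis on unrelated events | Reads as no, or at least not the focus |
| 5.3.15, 24-hour sentence | All SAEs | Yes |
| 6.1 | Any occurrence with a listed outcome | Yes |
| 6.2 | Causality assessed for each SAE | Yes; otherwise the assessment has little purpose |
| 2.7 | Missing or delayed SAE reporting is a major deviation | Yes, by way of 6.1 |

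Take a readmission for a surgical complication. It meets 6.1 through hospitalization. By the capture sentences it is a treatment-related complication and can be entered only there; by the other rules it must also be an SAE. The sections do not say which rule prevails, or that an event recorded as a complication must be reported as an SAE as well.

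**Step 2: can severity be obtained after surgery?**

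- Intra-operative events: yes, grades 0 to IV.
- Lymphatic effects: yes, CTCAE 3.0.
- Post-operative events reported as SAEs: an intensity is assessed (6.2), on no named scale.
- All other post-operative complications under 5.3.7: no grade.

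Major post-operative complications (9.3.3, 9.5) therefore have no definition, and the record that would supply them has no field from which to derive one. The two sections also word the threshold differently.

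**Step 3: how much could under-counting matter?** This is an illustration only. The 378 per arm comes from 7.2; every rate below is an assumption.

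Let u be the proportion of patients with an unrelated SAE (3% to 10%, equal in both arms), a and b the proportions with a related serious complication, and c the share of related events counted as SAEs. Treating the two kinds of event as additive, p1 = u + c·a and p2 = u + c·b. The approximate power of the two-sided 5% chi-squared test, in the direction of the true difference, is

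Φ[(|p2 − p1| − 1.96·SE0) / SE1],

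where SE0 = √[2·p̄(1 − p̄)/378], SE1 = √[(p1(1 − p1) + p2(1 − p2))/378] and p̄ = (p1 + p2)/2.

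Worked case, u = 5%, a = 5%, b = 10%:

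- c = 1: p1 = 0.10, p2 = 0.15, SE0 = 0.0241, SE1 = 0.0240. Power = Φ(0.12) = 55%.
- c = 0.5: p1 = 0.075, p2 = 0.10, SE0 = 0.0206, SE1 = 0.0205. Power = Φ(−0.74) = 23%.

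| Assumed related rates | All counted (c = 1) | Half counted (c = 0.5) | None counted (c = 0) |
|---|---|---|---|
| 5% vs 10% | 44–61% | 17–28% | about 3% |
| 8% vs 15% | 65–78% | 26–40% | about 3% |

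Ranges run over u from 10% down to 3%. The last column is the extreme case, not an expectation. It is about 3% because no difference is then left to detect.

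**The case against.** A reader might infer that serious surgical complications are excluded from the SAE data and escape the centre-closure provision. The protocol does not support that.

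- The capture sentences are introduced as additions to the complication record, and their emphasis on unrelated events is not a restriction to them. The 24-hour duty, 6.1 and 6.2 all bring related serious events in. The study calendar (5.1) and the surgery visit (5.2.3) list SAEs without qualification, and 2.7 makes missing reports a major deviation. A site that left such an event out would be in breach.
- Section 5.3.7 is more than a list of symptoms. Its opening instruction lets a wound problem, bleed or fistula be entered.
- It would be wrong to say that no post-operative severity is collected: SAEs carry an intensity, and lymphatic effects a CTCAE grade.
- Centre closure is discretionary, has a separate limb for poor surgical quality, and 9.5 adds audits and videos. A serious complication does not fall outside it.
- The SAE comparison is descriptive, so no confirmatory conclusion rests on it.

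All of this stands and narrows the point. It does not reconcile 2.3.2 and 5.3.15 with 6.1 and 6.2, provide a grade for most post-operative complications, or define major. The fuller list of event prompts that one might want in 5.3.7 is a matter of preference and not part of the finding.

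**Conclusion.** The point holds in two limited parts. First, the protocol contradicts itself on the scope of SAE capture. Read as a whole it includes treatment-related serious events, but two sections describe the capture otherwise, so under-counting is possible and may vary between sites. It would affect the descriptive comparison in 7.1.3 and the SAE rates available to the DMC. How much cannot be stated from the protocol: the power figures rest on assumed rates and on an assumed half of related events being left out, and show only that the reading chosen could matter. It cannot be inferred that related events will be absent.

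Second, post-operative complications have no common severity grade. Major complications therefore cannot be counted consistently across centres, and the arms cannot be compared on complication severity beyond SAE intensity and lymphatic effects.

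The primary endpoint analysis is not touched. The change should be made, because it decides what sites record.

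**What to change.** 1. In 2.3.2 and 5.3.15, remove the word *other* and the phrase on treatment relatedness from the SAE sentences. State that every event meeting 6.1 is reported as an SAE and enters the 7.1.3 comparison whatever its relation to surgery, including when it is also recorded as an intra- or post-operative complication.
2. In 5.3.7, add one named severity grade for each post-operative complication. CTCAE is one option, since the trial already uses it for lymphatic effects.
3. In 9.3.3 and 9.5, define major as a grade on that scale, chosen by the sponsor, and reconcile the two threshold wordings.

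The cost is protocol wording, one eCRF field at visits 4 to 6, and a few more SAE forms for sites. No visit or procedure is added. Prompts for specific perioperative events in 5.3.7 are optional.

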#### 6 ADVERSE EVENTS

#### 6.1 Definition of Serious Adverse Events

Serious Adverse Event Definition

A Serious Adverse Event (SAE) is defined as any undesirable medical occurrence according to the FDA definition:

- Results in death
- Is life threatening

Report if you suspect that the death was an outcome of the adverse event and include the date. Report if suspected that the patient was at substantial risk of dying at the time of the adverse event.

• Requires hospitalization (initial or prolonged)

Report if admission to the hospital or prolongation of hospitalization was a result of the adverse event. Emergency room visits that do not result in admission to the hospital should evaluated for one of the other serious outcomes (e.g., life-threatening; required intervention to prevent permanent impairment or damage; other serious medically important event).

• Results in disability or permanent damage

Report if the adverse event resulted in a substantial disruption of a person's ability to conduct normal life functions, i.e., the adverse event resulted in a significant, persistent or permanent change, impairment, damage or disruption in the patient's body function/structure, physical activities and/or quality of life.)

• Other serious (important medical events)

Report when the event does not fit the other outcomes, but the event may jeopardize the patient and may require medical or surgical intervention (treatment) to prevent one of the other outcomes. Examples include for instance the development of drug dependence or drug abuse as a result of the study treatment.

## 6.2 Adverse Event Monitoring and Reporting

#### SAE Monitoring

When an SAE occurs, it is the responsibility of the investigator to review all documentation (e.g., hospital progress notes, laboratory reports, and diagnostics reports) related to the event. The investigator will then record all relevant SAE information in the eCRF.

The investigator will attempt to establish a diagnosis of the event based on signs, symptoms, and/or other clinical information. Whenever possible, the diagnosis (not the individual signs/symptoms) will be documented as the SAE.

SAEs including a risk-benefit evaluation of the study by the responsible investigator will be reported periodically to the Ethics Committee according to the Declaration of Helsinki.

#### Assessment of Intensity and Causality

The investigator will assess the intensity for each SAE reported from day of surgery until the follow up visit 6. An event is defined as 'serious' when it meets at least one of the predefined outcomes as described in the definition of an SAE, NOT when it is rated as severe.

Furthermore, the investigator is obligated to assess the relationship between trial treatment and each occurrence of SAE. The investigator will use clinical judgment to determine the relationship. Alternative causes, such as underlying disease(s), concomitant therapy, and other risk factors, as well as the temporal relationship of the event to trial treatment will be considered and investigated. For each SAE, the investigator must document in the medical notes that he/she has reviewed the SAE and has provided an assessment of causality. The investigator may change his/her opinion of causality in light of follow-up information and send a SAE follow-up report with the updated causality assessment to the responsible investigator.

#### SAE Follow-Up

The investigator is obligated to perform or arrange for the conduct of supplemental measurements and/or evaluations as medically indicated to elucidate the nature and/or causality of the AE or SAE as fully as possible. This may include additional laboratory tests or investigations, histopathological examinations, or consultation with other health care professionals.

If a patient dies during participation in the trial or during a recognized follow-up period, the investigator will provide the responsible investigator with a copy of any postmortem findings including histopathology.

#### 7 STATISTICAL METHODS

## 7.1 Trial Objective and Hypotheses

#### 7.1.1 Hypotheses

The primary objective of the G-LACC trial is to demonstrate the non-inferiority of laparoscopic or robot-assisted radical/ hysterectomy (minimally invasive surgery) compared to abdominal hysterectomy (open surgery) with regard to diseasefree survival (DFS) in patients with early-stage cervical cancer. The non-inferiority margin defined for the hazard ratio (HR) for DFS (minimally invasive surgery / open surgery) is 2.3 (for more details about the non-inferiority margin, please see section 7.2). The statistical hypotheses are as follows:

$$\begin{split} H_0: \lambda_{minimal} / \lambda_{open} &= HR \geq 2.3 \\ H_1: \lambda_{minimal} / \lambda_{open} &= HR < 2.3 \end{split}$$

where  $\lambda_{minimal}$  and  $\lambda_{open}$  are the hazards for the primary endpoint event in the minimally invasive and open surgery arm, respectively.

As soon as the null hypothesis is rejected, the non-inferiority of minimally invasive surgery compared to open surgery with regard to DFS will be concluded.

## 7.1.2 Primary endpoint

The primary endpoint disease-free survival (DFS) will be analyzed according to the intention-to-treat (ITT) principle which includes all patients as randomized. The DFS curves will be estimated using the Kaplan-Meier method. A Cox proportional hazards model adjusted for the stratification factors for the randomization will be used for the comparison of minimally invasive and open surgery. Non-inferiority of minimally invasive as compared to open surgery will be declared if the upper boundary of the two-sided 95% CI for the hazard ratio (minimally invasive / open) is below the predefined non-inferiority margin of 2.3. A sensitivity analysis will be performed according to the per-protocol (PP) principle which includes all randomized patients where surgery has been performed according to the initial randomization. Consistency between results in the ITT and PP analysis is needed to draw meaningful conclusion regarding differences in DFS.

## 7.1.3 Secondary endpoints

Overall survival (OS) will be analyzed in line with the primary analysis of the primary endpoint.

Data for other secondary endpoints will be summarized by treatment groups, compared with appropriate statistical tests adjusted in line with the primary analysis of the primary endpoint.

Absolute and relative frequencies of serious adverse events (SAEs) will be displayed for the whole population and separately for each treatment group and comparisons between groups using Chi-squared tests will be performed and assessed descriptively.

Analyses of DFS and OS in relevant subgroups will also be performed for the following subgroups:

- tumor size (<2cm vs 2-<4 cm)
- sentinel node mapping only (yes vs no)
- radical vs simple hysterectomy (SHAPE criteria)

- anticipated type of minimally invasive surgery (laparoscopic vs robot-assisted)
- histological type (squamous cell carcinoma vs. adenocarcinoma, adenosquamous carcinoma)
- grading (G1-2 vs G3)
- center

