### Health care costs

Treatment costs and cost effectiveness will be determined as incremental cost-effectiveness ratios. Direct costs will be assessed via internal accounting and billing systems within the hospitals. The quality-adjusted life years (QALYs) gained with the intervention will be calculated based on health status measures for trial participants, with valuations of changes in health status and quality of life based on the EQ-5D questionnaire. QALY calculations will then be used for a cost-utility analysis.

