### 2.6 Randomization

A permuted block randomization with randomly selected block sizes will be conducted to allocate patients to both treatment arms in a 1:1 ratio. The randomization will be stratified by the following factors:

- tumor size (<2cm vs 2-<4 cm)
- sentinel node mapping only (Yes vs No)
- radical vs simple hysterectomy (SHAPE criteria)
- anticipated type of minimally invasive surgery (laparoscopic vs robot-assisted)
- center

Treating physicians will determine the type of minimally invasive surgery (laparoscopic or robot-assisted) upfront randomization to enable stratification. The type of laparoscopic surgery, whether conventional or robotic, is determined by the surgeon based on the surgeon's experience and preference. If a simple hysterectomy is to be considered for patients with low-risk early-stage cervical cancer meeting the SHAPE-criteria (tumor < 2cm, < 10 mm depth of stromal invasion (LEEP/cone) this must already be determined before the randomization process.

Randomization will only be performed after verification of the patient's eligibility and signed written informed consent. All inclusion criteria and no exclusion criteria must be met. Furthermore, baseline assessment of quality of life questionnaires will be performed prior to randomization.

Patients will be randomized using the electronic randomization tool provided within the eCRF/electronic data capture (EDC) system.

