## 5.3.12 Quality of Life Assessments

In order to compare the grade of short- and long-term effects on the patients' HRQoL between both treatments (ARH und LRH) all participants will be asked to complete QoL questionnaires at different times over the course of the trial. The QoL assessments' focus will be on late side-effects such as bladder dysfunction, sexual activity, physical-, emotional, and role functioning as well as fatigue and pain.

Patients will complete HRQoL questionnaires in an appropriate language either as electronical patient reported outcome measures or during the clinic visits (by manually filling in hardcopy forms, by accessible computer (eCRF) or by mail). Study personnel, e.g. investigator or study nurses, will not have access to the QoL-forms while answered by the patient in order to avoid any influence.

Eligible patients will be informed orally and in writing about the HRQoL assessment before inclusion in the trial. Baseline assessment will be performed before randomisation to one of both treatment arms at visit 1 but only after written and oral informed consent is obtained. Post-surgery assessments will be conducted 1 and 6 months as well as 1, 2, 3, 4 and 5 years after treatment at visits 4 to 10 (see section 5.1). Completed questionnaires will be collected either in connection to the visit at the clinic, electronically via eCRF or per conventional mail and are always considered as source documents.

The following questionnaires will be completed by all patients included in the G-LACC trial as stated above (see Appendix 0):

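### The adjustment rule in Protocol 7.1.3 does not name the visit 1 score, so the quality-of-life and EQ-5D comparisons, applied as written to follow-up scores, lose precision

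*Protocol*

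**What the plan says.** Protocol 7.1.3 gives one rule for all secondary endpoints other than overall survival: they are summarized by arm and "compared with appropriate statistical tests adjusted in line with the primary analysis of the primary endpoint". The primary analysis in 7.1.2 is "A Cox proportional hazards model adjusted for the stratification factors for the randomization". Section 2.6 lists those factors: tumor size, sentinel node mapping only, radical or simple hysterectomy, anticipated laparoscopic or robot-assisted surgery, and center.

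On the timing of the questionnaires, 2.6 says that "baseline assessment of quality of life questionnaires will be performed prior to randomization", and 5.3.12 says that "Baseline assessment will be performed before randomisation to one of both treatment arms at visit 1". The study calendar in 5.1 names QLQ-C30, QLQ-CX24, EQ-5D-3L and SAQ for that visit and allows randomization only after the quality-of-life questionnaires are completed. Follow-up is frequent: "Post-surgery assessments will be conducted 1 and 6 months as well as 1, 2, 3, 4 and 5 years after treatment".

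EQ-5D also feeds the economic endpoint. Under Health care costs (2.3.2), "The quality-adjusted life years (QALYs) gained with the intervention will be calculated based on health status measures for trial participants".

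**The concern.** The rule was written for disease-free survival, a time-to-event outcome with no baseline value, and then carried over to repeated scores that do have one. A patient's score before surgery usually predicts her later scores. Tumor size, surgical plan and center do not stand in for it.

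At stake is the benefit side of the trial's argument. Sections 1.5 and 1.6 set the possible oncologic risk of minimally invasive surgery against fewer complications, better recovery and better quality of life. Section 1.4 reports that the LACC trial found no quality-of-life gain. Section 5.3.12 makes the comparison of short- and long-term quality of life between arms the purpose of the questionnaires. Wider intervals than necessary on these endpoints weaken that comparison and the cost-utility analysis built on EQ-5D.

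**Working it through.** **1. What the rule resolves to.** 7.1.3 points to 7.1.2, and 7.1.2 points to the factors in 2.6. None of the five is a patient-reported score. Four instruments have a visit 1 value. No section names that value as a covariate.

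**2. The plan's own figure.** The protocol states no power or precision for quality of life. Its only sizing is for disease-free survival (7.2): hazard ratio margin 2.3, one-sided 2.5%, power 80%, event probability 6%.

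- Events: 4 × (1.960 + 0.842)² / (ln 2.3)² = 45.26, stated as 45. Power at 45 events is 79.8%.
- Patients: 45.26 / 0.06 = 754.3, which rounds up to 378 per arm, 756 in total.

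This reproduces, and the present point does not touch it.

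**3. Effect of adding the visit 1 score.** Inputs: 378 per arm (7.2) and 1:1 allocation (2.6). Assumed, because the protocol gives no value: correlation ρ between visit 1 and follow-up score of 0.3 to 0.7, and an illustrative arm difference of 0.2 SD tested two-sided at 5%. SD and ρ are taken as those remaining after the stratification factors.

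- SE without baseline, in SD units: √(2/378) = 0.0727
- SE with baseline: 0.0727 × √(1 − ρ²)
- Equivalent unadjusted size per arm: 378 / (1 − ρ²)
- Power: Φ(0.2/SE − 1.96)

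| ρ (assumed) | SE | Variance cut | 95% CI narrower by | Equivalent n per arm | Power, 0.2 SD |
|---|---|---|---|---|---|
| not adjusted | 0.0727 | – | – | 378 | 78.5% |
| 0.3 | 0.0694 | 9% | 5% | 415 | 82.2% |
| 0.5 | 0.0630 | 25% | 13% | 504 | 88.8% |
| 0.7 | 0.0519 | 49% | 29% | 741 | 97.1% |

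If 80% of questionnaires are returned (also assumed; 378 × 0.8 ≈ 302 per arm), power is 69.1% unadjusted against 73.2%, 81.1% and 93.1%.

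**4. Chance imbalance.** The visit 1 difference between arms has standard deviation 0.0727 SD, so a 95% range of ±1.96 × 0.0727 = ±0.143 SD. Without baseline adjustment about ρ times that stays in the estimate: up to 0.04, 0.07 or 0.10 SD at ρ = 0.3, 0.5 or 0.7.

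**5. Change scores as an alternative.** The variance of a change from baseline, relative to the raw follow-up score, is 2(1 − ρ): 1.4, 1.0 and 0.6 at ρ = 0.3, 0.5 and 0.7. With the baseline as covariate it is 0.91, 0.75 and 0.51. At ρ of 0.5 or below, change scores are no better than ignoring baseline.

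**The case against.** The strongest reply is that 7.1.3 carries over an adjustment without forbidding a further covariate, and that the quality-of-life model is the kind of detail a statistical analysis plan supplies. A repeated-measures model with the visit 1 score as one of the outcomes would also satisfy 7.1.3 and recover essentially the same precision. This stands to the extent that a reader may not infer that baseline adjustment is excluded. The loss arises only if the stated set is used on follow-up scores and nothing more is done. It does not remove the point, because the protocol does state an adjustment set, and a better one is available from data already required.

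Four other stronger readings are not supported:

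- *All quality-of-life instruments have a baseline.* LYMQOL is completed only by patients who report lymphedema (5.1, 5.3.13). QLQ-CX24 items 50 to 54 and SAQ section III are answered only by sexually active women, so their visit 1 values will be absent for an unknown number.
- *The estimates are biased.* Randomization keeps the unadjusted difference unbiased on average, and its interval already allows for chance imbalance.
- *Baseline utility is ignored in the QALYs.* The health care costs text refers to changes in health status, so baseline may enter the calculation, although no baseline-adjusted comparison of arms is stated.
- *A definite QALY distortion can be quoted.* With an assumed utility SD of 0.2 and ρ of 0.5 to 0.7 held for five years, a one-SE imbalance gives 0.2 × 0.0727 × 5 × ρ ≈ 0.04 to 0.05 QALY. That rests wholly on assumed values, with a correlation unlikely to hold for five years, and serves only as an upper illustration.

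**Conclusion.** The point holds in a limited form. As written, the adjustment for the non-survival secondary endpoints leaves out the visit 1 score of four instruments that must be completed before randomization. Applied to follow-up scores, that forgoes a variance reduction of 9% to 49% over the assumed correlations. At 0.3 the gain is small, about 5% of interval width; from 0.5 upward it is worthwhile. The power figures are illustrations, because the protocol sets no quality-of-life target difference, power or confirmatory claim. The consequence is confined to secondary endpoints. A change is worth making because it costs almost nothing, not because the trial's main conclusion is at risk.

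**What to change.** Add to Protocol 7.1.3:

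> *For patient-reported scores with a visit 1 value (QLQ-C30, QLQ-CX24, EQ-5D-3L, SAQ), arms are compared by a linear (mixed) model adjusted for the stratification factors and the visit 1 value of the same score. The QALY difference is adjusted for visit 1 EQ-5D utility. LYMQOL, and the SAQ and QLQ-CX24 scales answered only by sexually active women when the visit 1 value is not applicable, are excepted and are adjusted for the stratification factors only.*

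The cost is this text and a rule for missing or not-applicable visit 1 scores, which should keep the two cases apart: a not-applicable score should not simply be imputed. No new data, visits or patients are needed. In an open-label trial, fixing the covariate before outcome data are seen also rules out a later data-driven choice.
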